Prospective Case Series on a Combination Methylene Blue, Gentian Violet, and Ovine Forestomachderived Extracellular Matrix Dressing for Hidradenitis Suppurativa

NCT04354012

IRB Approval Date: 6/14/2021

Study Title: Prospective case series on the use of methylene blue, gentian violet, and ovine forestomach-derived extracellular matrix wound dressings for Hidradenitis Suppurativa

Principal Investigator: [name]

Sponsor or funding source: Departmental (dressings provided by Appulse Medical)

Background, Rationale and Context

Hidradenitis suppurativa (HS) is a chronic and debilitating inflammatory disease most frequently affecting the axilla, groin, and inframammary regions. Symptoms include nodules, abscesses, sinus tract formation, malodorous drainage, and scarring. These symptoms interfere with everyday activities, which can lead to social embarrassment and isolation. Patients with HS suffer psychological effects, such as increased levels of anxiety, depression, and loneliness, which impair quality of life. 3,4

Patients suffer with the burden of at home wound care for recurrent, draining nodules. Persistent lesions affect patients' lives by limiting their daily activities. Currently, patients are instructed to use gauze and tape to cover draining wounds, but this can be insufficient and difficult due to the nature and location of lesions associated with HS. Patients suffer with caring for their wounds, which can lead to frustration. Providing patients with a standard wound care regimen to take home can improve patients' quality of life and control of their disease. General recommendations for wound care in HS patients are limited. Improvements in the standard of care for wound management in HS are needed to aid patients.⁵

Objective

The objective of this case series is to monitor time and outcome of healing of wounds associated with HS using Endoform [ovine forestomach], Hydrofera Blue [methylene blue and gentian violet], and Hypafix tape.

Methods and Measures

Design

This will be a single-center, case series evaluating the length of time wound healing occurs using methylene blue, gentian violet, and ovine forestomach wound dressings to HS lesions. Patients of Wake Forest Dermatology clinic with a diagnosis of HS with draining nodules and open wounds will be recruited in clinic. Participants will be provided with methylene blue, gentian violet, and ovine forestomach products at screening/baseline visit. Lesions will be measured and recorded. Participants will complete a Numerical Rating Scale of Patient Reported Pain (NRS/Appendix I). Upon enrollment, participants will be provided with a standard cleansing protocol to be followed at home including using antibacterial soap prior to applying wound dressings. Dressings are to be changed every 3 days. In addition, they will be instructed to avoid bleach baths or acidic products for the duration of their involvement in the study. After visit 1, participants will return for follow-up at week 1, week 2, week 4, and week 8. At each visit, wounds will be measured and photographed, NRS will be completed, and participants will be provided with wound dressing products as needed.

Setting

Wake Forest Baptist Health Department of Dermatology Clinic during scheduled follow-up appointments. All study procedures will occur in-person.

Subjects selection criteria

• Inclusion Criteria

Protocol version:

Template updated 9.24.14

- o Individuals with hidradenitis suppurativa with non-healing wounds or draining abscesses/nodules
- o Individuals over 18 years of age

• Exclusion Criteria

- o Individuals younger than 18 years of age
- o Individuals without a diagnosis of HS

• Sample Size

 10 participants will be provided with wound care dressings from Appulse Medical.

Interventions and Interactions

Methylene blue, gentian violet, and ovine forestomach wound dressings will be provided by Appulse Medical. These wound care products are used for local management of wounds. This study is monitoring the impact these wound care products have on wounds associated with HS. Additionally, NRS assessments will be administered to evaluate the impact wound healing has on patient reported pain.

Endoform (ovine forestomach) is a natural dermal template used in all phases of wound healing. This product helps to stabilize, build, and organize tissue in acute and chronic wounds.

Hydrofera Blue is an antibacterial foam dressing that contains methylene blue and gentian violet to manage wounds. This is a safe, non-cytotoxic product that can be worn for 7 days while not inhibiting growth factors. This products wicks bacteria into the foam and away from the wound surface using natural negative pressure through capillary flow.

Hypafix tape aids in stabilization of wound dressings. This product is easy to apply, skin friendly, and comfortable to use.

Screening Visit/Visit 1

- Informed consent will be obtained
- Photographs of wounds at baseline will be taken
- Wounds will be measured, and appropriate amount of wound dressings will be administered and application instructions will be provided
 - o Clean the wound with antibacterial soap.
 - Apply Endoform dermal template first, trimming it to fit the lesion, followed by Hydrofera Blue and fixed using Hypafix tape.
- Basic demographics, BMI, and smoking history will be recorded
- Participants will receive a standardized cleansing regimen to follow at home (Appendix II)
- Completion of NRS
- Completion of Dermatology Life Quality Index (DLQI/Appendix III)
- Completion of Sartorius Hidradenitis Suppurativa Score (Appendix IV)

Visits 2, 3, 4, 5

- Photographs of wounds at baseline will be taken
- Previous and new wounds will be measured, and appropriate amount of wound dressings will be administered
- Completion of NRS
- Completion of DLQI
- Completion of Sartorius Hidradenitis Suppurativa Score

Outcome Measure(s)

- 1. Assess the time for wound healing to occur using Endoform and Hydrofera Blue products.
- 2. Asses the percent healing that occurs over 8 weeks of follow-up using Endoform and Hydrofera Blue products.
- 3. Assess changes in patient reported pain via NRS
- 4. Assess changes in Sartorius scale

Analytical Plan

Wound area will be calculated by measuring length multiplied by width of the lesions. Wounds will be measured at each visit, and percent (%) change in area of lesion will be recorded.

Time versus % area healed will be analyzed. Post hoc analyses will be conducted to explore the relationship between participants' self-report on psychosocial measures and wound healing time.

Results will be analyzed initially using descriptive statistics. Comparison between groups will be done using chi square tests for proportions, and t-tests or ANOVA procedures for continuous variables. Regression analysis will be performed to identify independent outcome predictors. Other inferential statistical analysis will be conducted as appropriate.

Human Subjects Protection

All information provided will be kept confidential. Subjects will remain deidentified.

Subject Recruitment Methods

Subjects who meet the inclusion and exclusion criteria will be eligible for participation in this study. Participants will be recruited from the Wake Forest Department of Dermatology clinic by either the PI or members of the study team.

Informed Consent

Written informed consent will be obtained by members of the study team. The risk of harm or discomfort that may occur as a result of taking part in this research study is not expected to be more than in daily life or from routine physical or psychological examinations or tests. The rights and welfare of study will be protected through the use of measures to maintain the confidentiality of study information. Study results will be presented or published in lieu of providing individual subjects additional information regarding the study.

Confidentiality and Privacy

Confidentiality will be protected by collecting only information needed to assess study outcomes, minimizing to the fullest extent possible the collection of any information that could directly identify subjects, and maintaining all study information in a secure manner. To help ensure subject privacy and confidentiality, only a unique study identifier will appear on the data collection form. Any collected patient identifying information corresponding to the unique study identifier will be maintained on a linkage file, store separately from the data. The linkage file will be kept secure, with access limited to designated study personnel. Following data collection subject identifying information will be destroyed 3 years, consistent with data validation and study design, producing an anonymous analytical data set. Data access will be limited to study staff. Data and records will be kept locked and secured, with any computer

data password protected. No reference to any individual participant will appear in reports, presentations, or publications that may arise from the study.

Data and Safety Monitoring

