Appendix I- Numerical Rating Scale of Pain (NRS)

Numerical Rating Scale of Pain
Subject Visit: □V1-Baseline □V2- Week 1 □V3- Week 2 □V4-Week 4 □V5- Week 8

Please mark on the scale below your level of pain:

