Appendix II- Cleansing regimen

When to change your dressing:

- Your dressing must be changed at least every 3 days.
- Change your dressing if the Hydrofera Blue foam has turned white or is visibly soiled.

To change your dressing:

- 1. Cleanse gently with antibacterial soap. We recommend Dial soap.
- 2. Dry well after showering.
- 3. After cleansing, apply Endoform dermal template first, trimming it to fit the wound.
- 4. Apply Hydrofera Blue on top of Endoform dermal template.
- 5. Fix the dressing in place with Hypafix tape if not using Hydrofera Blue products containing adhesive.

Please avoid using bleach baths and acidic products for the duration of the study.

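### Wound closure is known only to within visit gaps of 1, 1, 2 and 4 weeks, and the plan gives no method for dating healing inside those gaps

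*Combined protocol and SAP*

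**What the plan says.** The Design section gives the schedule: "After visit 1, participants will return for follow-up at week 1, week 2, week 4, and week 8". The visit labels in Appendix I agree ("V4-Week 4 □V5- Week 8"). Wound assessment is tied to these visits: "At each visit, wounds will be measured and photographed". The Setting section adds "All study procedures will occur in-person". No home diary or home photograph is planned.

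Outcome 1 is "Assess the time for wound healing to occur using Endoform and Hydrofera Blue products". Outcome 2 is the "percent healing that occurs over 8 weeks of follow-up". The Analytical Plan relates time to percent area healed and adds a post hoc look at psychosocial self-report against healing time. The methods named are descriptive statistics, chi-square tests, t-tests or ANOVA, and regression, with other inferential methods left open. The plan has no rule for assigning a healing date and names no interval-censored method.

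Appendix II, which participants take home, says "Your dressing must be changed at least every 3 days". Nothing noticed at those changes is recorded.

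**The concern.** A wound seen open at one visit and closed at the next healed at some unknown time in between. Without a rule, the natural choice is the date of the visit at which closure is first seen. Recorded healing times could then take only four values: 1, 2, 4 or 8 weeks. A wound closing on day 29 and one closing on day 55 would both be recorded at day 56, an overstatement of 27 days and 1 day.

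This error always runs upward, and in absolute terms it grows as the gaps widen. It would lengthen the reported healing time, which is the main result of a 10-participant case series. It would also add distortion to the post hoc analysis that uses healing time.

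**Working it through.** The plan states no figure on this point, so there is none to reproduce.

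**Inputs from the documents.** Visits at weeks 0, 1, 2, 4 and 8 (Design; Appendix I). Dressing changes at least every 3 days (Appendix II).

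**Assumptions.** Healing is dated at the first visit where the wound is seen closed. The wound is present at baseline, so its clock starts at visit 1. The documents give no healing distribution, so a range is shown.

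**1. Gaps.** 1 − 0 = 1, 2 − 1 = 1, 4 − 2 = 2 and 8 − 4 = 4 weeks. The last is 4/8 = 50% of follow-up.

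**2. Overstatement with closure uniform within a gap of length L.** The mean is L/2 and the maximum is L. The means are 0.5, 0.5, 1.0 and 2.0 weeks.

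**3. Overstatement with exponential healing.** With rate λ = ln 2 / median, the mean overstatement in a gap is L − [1/λ − L·exp(−λL)/(1 − exp(−λL))]. For a true median of 4 weeks, λ = 0.1733 per week. The results are 0.514 week (3.6 days) in each of the first two gaps, 1.058 weeks (7.4 days) in weeks 2-4 and 2.229 weeks (15.6 days) in weeks 4-8.

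**4. Mean healing time among wounds healed by week 8, true median 4 weeks.** The shares closing in the four gaps are 0.2121, 0.1784, 0.2761 and 0.3333.

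- Recorded mean: 0.2121×1 + 0.1784×2 + 0.2761×4 + 0.3333×8 = 4.34 weeks.
- Excess: (0.2121 + 0.1784)×0.514 + 0.2761×1.058 + 0.3333×2.229 = 1.24 weeks.
- True mean: 4.34 − 1.24 = 3.10 weeks.
- Midpoint-dated mean: 0.2121×0.5 + 0.1784×1.5 + 0.2761×3 + 0.3333×6 = 3.20 weeks.

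The same steps for other medians (weeks):

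| True median | True mean | Visit-dated mean | Excess | Midpoint-dated mean |
|---|---|---|---|---|
| 2 | 2.35 | 3.42 | 1.07 | 2.49 |
| 3 | 2.83 | 4.01 | 1.18 | 2.95 |
| 4 | 3.10 | 4.34 | 1.24 | 3.20 |
| 6 | 3.39 | 4.68 | 1.29 | 3.47 |

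**5. Error left in individual dates (median 4 weeks).**

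- Midpoint dating: taking closure as uniform within each gap, the mean square error is Σ share×L²/12 = (0.3905×1 + 0.2761×4 + 0.3333×16)/12 = 0.569. The root is 0.754 week, about 5.3 days.
- Take-home sheet: if closure is noted at the next 3-day dressing change, and entries are complete and accurate, the mean error is 3/2 = 1.5 days and the root mean square error is 3/√3 = 1.7 days.

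**6. Proportional error.** Under the uniform assumption, overstatement divided by mid-gap time is 0.5/0.5 = 100% in weeks 0-1. It is then 0.5/1.5, 1.0/3 and 2.0/6, which is 33% each time.

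**The case against.** The strongest reply is that the bias comes from a dating rule the documents do not contain. The stated analysis of time against percent area healed uses areas measured at known visit times, so it has no rounding-up error. Midpoint dating of the same visits removes nearly all the mean bias (3.20 against 3.10 weeks). In simulation with a median of 4 weeks, true and visit-dated times correlate at 0.94, so the harm to an exploratory association in 10 participants is small. All of this stands. It makes the point a missing method rather than a faulty visit schedule. It does not remove the point, because outcome 1 is a time to an event and nothing in the plan prevents visit dating.

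Two stronger readings are tempting, and the documents support neither.

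- *Late healing dates are disproportionately wrong.* The rise is absolute: about 4-fold from weeks 0-2 to weeks 4-8, but only about 2-fold from weeks 2-4. Proportionally the error is largest in week 1 and roughly flat afterwards.
- *New wounds in weeks 4-8 mostly go unseen*, given that at Visits 2 to 5 "Previous and new wounds will be measured, and appropriate amount of wound dressings will be administered". This needs a short wound duration that the documents do not give. For onset uniform in a 4-week gap and exponential duration with mean m, the share still open at week 8 is (m/4)(1 − exp(−4/m)). That is 43% for m = 2 weeks. Healing medians of 2 to 6 weeks (m = 2.9 to 8.7) give 54% to 80%, a majority seen. New-wound counts are also not a listed outcome. The Appendix IV form, completed at week 8, asks for boils in the latest month, which would count some by recall.

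**Conclusion.** The point holds as a gap in the analysis plan with an inexpensive improvement available. If closure is dated at the visit, outcome 1 is overstated on average by about 0.5, 1 and 2 weeks for closures in weeks 0-2, 2-4 and 4-8, and the mean among wounds healed by week 8 is 1.1 to 1.3 weeks too long. These sizes rest on visit dating, which is likely but unstated, and on exponential healing with true medians of 2 to 6 weeks. The uniform calculation gives nearly the same figures by gap. A reader might infer that the schedule itself invalidates the outcome or that more visits are required. Neither follows, since the present visits support an interval-based estimate with little mean bias.

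**What to change.** **Analysis.** State in the Analytical Plan that healing time is interval-censored between the last visit at which the wound was seen open and the first at which it was seen closed. At the least, date it at the interval midpoint. Do not use the visit date as the healing time. This needs no new data.

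**Data, to narrow the intervals.** Number the wounds and add a dated line per wound to the Appendix II sheet, on which the participant writes the date the wound is first seen closed at a dressing change. Use that date only when the next visit confirms closure, and keep the visit interval when it is missing. Report the visit-interval results as a sensitivity analysis. Amend the Setting statement "All study procedures will occur in-person" to allow the sheet.

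**Cost.** A short amendment, a wound-numbering step at visits and an extra entry on an existing sheet, with no added visit or staff. The dates are self-reported, some will be missing, and they will be harder to obtain for sites the participant cannot easily see, such as the gluteal regions listed in Appendix IV. Clinic confirmation should therefore remain the test of closure.

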Appendix III

DE	RMATOLOGY LIFE QUALITY INDEX			DLQI
Nar	me: Date:		Score:	
	e aim of this questionnaire is to measure how much your our life OVER THE LAST WEEK. Please check one box for	•	as affect	ed
1.	Over the last week, how itchy , sore , painful or stinging has your skin been?	Very much A lot A little Not at all		
2.	Over the last week, how embarrassed or self conscious have you been because of your skin?	Very much A lot A little Not at all		
3.	Over the last week, how much has your skin interfered with you going shopping or looking after your home or yard?	Very much A lot A little Not at all	Not rele □	vant
4.	Over the last week, how much has your skin influenced the clothes you wear?	Very much		

Protocol version:

		A lot A little Not at all	Not relevant □
5.	Over the last week, how much has your skin affected any social or leisure activities?	Very much A lot A little Not at all	Not relevant □
6.	Over the last week, how much has your skin made it difficult for you to do any sport ?	Very much A lot A little Not at all	Not relevant □
7.	Over the last week, has your skin prevented you from working or studying?	yes no	Not relevant □
	If "No", over the last week how much has your skin been a problem at work or studying ?	A lot A little Not at all	
8.	Over the last week, how much has your skin created problems with your partner or any of your close friends or relatives ?	Very much A lot A little Not at all	Not relevant □
9.	Over the last week, how much has your skin caused any sexual difficulties?	Very much A lot A little Not at all	Not relevant □
10	Over the last week, how much of a problem has the treatment for your skin been, for example by making your home messy, or by taking up time?	Very much A lot A little Not at all	Not relevant □

Please check you have answered EVERY question. Thank you.

 $^{\scriptsize{\textcircled{C}}}$ AY Finlay, GK Khan, April 1992, This must not be copied without the permission of the authors.

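### Pain (NRS) is listed after wounds are photographed and measured, with no instruction to rate it before they are uncovered, so handling pain may enter the change score.

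*Combined protocol and SAP*

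**What the plan says.** The Design section (Methods and Measures) describes baseline in this order: products are supplied ("Participants will be provided with methylene blue, gentian violet, and ovine forestomach products at screening/baseline visit"), lesions are measured, and the NRS is completed. For study visits generally it says "At each visit, wounds will be measured and photographed, NRS will be completed", and the same sentence then turns to the supply of dressing products.

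The Visit 1 list under Interventions and Interactions has consent, photographs, and then "Wounds will be measured, and appropriate amount of wound dressings will be administered and application instructions will be provided". Demographics and the cleansing regimen follow, and only then "Completion of NRS", the DLQI and the Sartorius score. The Visits 2, 3, 4, 5 list has photographs, then "Previous and new wounds will be measured, and appropriate amount of wound dressings will be administered", then the NRS, DLQI and Sartorius score.

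The prompt on the NRS form (Appendix I) is "Please mark on the scale below your level of pain". It does not ask for pain now, on average, or at its worst over a period. The DLQI form (Appendix III) does set a period, for example "Over the last week, how itchy , sore , painful or stinging has your skin been".

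Outcome Measure(s) lists change in NRS pain third of four. The DLQI is not among the four.

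**The concern.** A covered wound cannot be photographed or measured. From Visit 2 onwards participants should be wearing the study dressing: Endoform under Hydrofera Blue foam, held by tape or by an adhesive version of the foam. If staff follow the order in which the protocol lists the steps, the dressing comes off and the wound is handled before the participant is asked about pain. With no recall period in the prompt, some participants may rate the pain of that moment rather than the pain of their disease.

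This is a single-arm series, so no comparison group would share the procedural component and remove it. The protocol also wants to use the NRS to learn how healing affects pain. A pain score that partly reflects what was done to the wound minutes before is a poorer measure for that purpose, and it cannot be corrected once the data are collected.

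**Working it through.** The plan has no figure to reproduce here. The check sets the places side by side and then asks what enters the change score.

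**Order of steps**

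| Place | Listed before NRS | Listed after NRS |
|---|---|---|
| Design, baseline | product supply, measurement | cleansing instructions |
| Design, each visit | measurement, photographs | product supply |
| Visit 1 list | consent, photographs, measurement with dressings and instructions, demographics, cleansing regimen | DLQI, Sartorius |
| Visits 2–5 list | photographs, measurement with dressings | DLQI, Sartorius |

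All four rows put measurement before the NRS. They disagree on two other things: whether photographs precede measurement, and, at follow-up, whether dressings are supplied before or after the NRS. No section gives a different place for the NRS.

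**What enters the change score**

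Let T be the participant's pain without handling, and h the amount that uncovering and handling add to the rating. At follow-up visit k:

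observed change = (T_k + h_k) − (T_1 + h_1) = (T_k − T_1) + (h_k − h_1)

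- If h_k = h_1, the handling effect cancels and the mean change is unbiased.
- If h_k > h_1, the observed change is shifted towards more pain, which may hide a benefit.
- If h_k < h_1, it is shifted towards less pain, which may create an apparent benefit.
- If the NRS comes first at every visit, h is zero throughout and the question does not arise.

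Averaging over follow-up visits leaves the mean of (h_k − h_1). A shift that recurs at each visit is not reduced by averaging.

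**Can the sign be fixed from the documents?** No. The Background says patients are currently told to use gauze and tape, so a covering may also come off at Visit 1 and h_1 need not be zero. The covering at follow-up is a different one, so h_k need not equal h_1.

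**Scale, on assumed values only.** The documents give no SD for NRS change. Assume 2 to 3 points and 10 complete pairs. Then SE = SD/√10, which is 2/3.162 = 0.63 to 3/3.162 = 0.95 points. A net handling difference of 1 point, if there were one, would be 1/0.95 = 1.1 to 1/0.63 = 1.6 standard errors. This shows only what such a difference would mean in a series of 10. It is not an estimate of the difference.

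**The case against.** The strongest reply is that the visit lists are unnumbered and are nowhere declared to be a timed sequence. Where order matters, the protocol marks it: Appendix II numbers its steps, and the application instructions say which product goes on first. Read literally, the Design text would supply products before lesions are measured. In-clinic dressing removal is never described. This stands in part. It is not established that follow-up ratings *will* contain removal pain, only that nothing prevents it. An unspecified order leaves timing free to vary between visits and participants, and the only order staff can read puts the NRS after measurement.

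A reader might infer several stronger points that the documents do not support:

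- *Baseline is taken after the first dressing.* The wording about administering dressings may mean dispensing them for home use, and the Design text speaks of providing products. At follow-up the Design text puts the NRS before supply.
- *Participants rate pain after learning whether the wound shrank, giving a second bias in the opposite direction.* No section says measurements are shared. Participants change their own dressings at home and already see their wounds, and reordering the visit would not alter that.
- *The DLQI is affected in the same way.* Its items refer to the last week, which makes it largely insensitive to order within a visit. It is not a listed outcome, and the Design text does not mention it.
- *Handling pain necessarily masks a benefit, by a calculable share of the confidence interval.* Baseline NRS also follows measurement, so the sign is open. Any such share would divide one assumed value by another.

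It is also fair to say that the scale graphic in Appendix I is not shown in the public text, so a recall period printed on the scale itself cannot be ruled out.

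**Conclusion.** The point holds in a limited form. The Design text and both visit lists place the NRS after wound measurement, no section requires it before wounds are uncovered, and the visible prompt has no recall period. Pain from removal and handling may therefore enter the third listed outcome. The bias in mean change is the difference in handling effect between follow-up and baseline. That difference need not be zero, because the coverings differ, but its direction and size cannot be determined from the documents.

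The conclusion rests on two inferences: that wounds are uncovered in clinic in order to be measured, and that staff may work in the order listed. It does not touch the wound-healing outcomes, which are the main objective.

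**What to change.** In the Design text and in both visit lists, make the NRS the first step after arrival (after consent at Visit 1). It should come before any dressing is removed or applied and before wounds are handled, photographed or measured, in the same order at all five visits. At the same time, reconcile the Design text with the visit lists on the order of photographs, measurement, NRS and dressing supply.

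The DLQI may be moved along with the NRS for convenience, though its one-week recall gives little statistical reason to do so. If Appendix I does lack a recall period, stating one would be a useful clarification, but the change of order does not depend on it.

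The cost is a reordered checklist, with no added procedure or visit time and no other downside. If visits have already taken place, the report should state when the NRS was completed relative to uncovering the wounds, or that this was not recorded.

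### Time to healing is the first outcome, but no named method accounts for wounds still open when follow-up ends, whether present at Visit 1 or first seen later

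*Combined protocol and SAP*

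**What the plan says.** Outcome 1 under Outcome Measure(s) is "Assess the time for wound healing to occur using Endoform and Hydrofera Blue products". Outcome 2 is "Asses the percent healing that occurs over 8 weeks of follow-up using Endoform and Hydrofera Blue products". The Design section sets the schedule: "After visit 1, participants will return for follow-up at week 1, week 2, week 4, and week 8". Under Visits 2, 3, 4, 5 the wounds to be measured include ones not present at baseline: "Previous and new wounds will be measured, and appropriate amount of wound dressings will be administered".

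The Analytical Plan says "Wounds will be measured at each visit, and percent (%) change in area of lesion will be recorded" and "Time versus % area healed will be analyzed". On methods it says "Results will be analyzed initially using descriptive statistics", then "Comparison between groups will be done using chi square tests for proportions, and t-tests or ANOVA procedures for continuous variables". It adds a regression of unspecified type to look for predictors, and a general clause allowing further inferential analysis where suitable.

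The documents do not say which wounds enter outcome 1 or outcome 2, when the clock starts for a wound first seen after Visit 1, which measurement is its reference area, or what is done with a wound that has not healed by its last visit. The general clause names no time-to-event method.

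**The concern.** For a wound still open at its last visit, the healing time is known only to exceed the time observed. If such wounds are left out, the mean describes only the faster healers and the series reports healing as quicker than it was. If they are counted as unhealed in a simple proportion, wounds with different amounts of follow-up are treated as equal.

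Both problems exist for Visit 1 wounds, which are cut off at 8 weeks. They are sharper for new wounds, which have less time to heal. The Design section puts the length of healing time at the centre of the study, so this is the figure readers will take away. Without a stated wound set and time origin, two analysts could also report different values for outcomes 1 and 2 from the same measurements.

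**Working it through.** **Plan's own figure.** None can be reproduced. The only number is 10 participants, given without a rate, effect size or error level. The number of wounds is not given.

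**Step 1. Follow-up available (schedule only, no assumption).** Visits fall at weeks 0, 1, 2, 4 and 8. For a wound first seen at week w, follow-up is 8 − w.

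| First seen (week) | Weeks left | Later measurements |
|---|---|---|
| 0 | 8 | 4 |
| 1 | 7 | 3 |
| 2 | 6 | 2 |
| 4 | 4 | 1 |
| 8 | 0 | 0 |

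Only Visit 1 wounds can have the full 8 weeks. A wound first seen at week 8 can have neither a percent change nor a healing time.

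**Step 2. Illustration (assumed, not in the documents).** All wounds heal at the same exponential rate with median m weeks. The central value is m = 6, with a range of 4 to 12. Healing is recorded at the first visit after it happens.

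- True mean = m / ln 2. For m = 4, 6 and 12 this is 5.8, 8.7 and 17.3 weeks.
- Share of Visit 1 wounds healed by week 8 = 1 − 0.5^(8/m). This is 75%, 60% and 37%, so 25%, 40% and 63% are still open.
- Mean recorded time among healed wounds = Σ(visit week × probability of first being found healed at that visit) / share healed.

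For m = 6 the probabilities of first being found healed at weeks 1, 2, 4 and 8 are 0.109, 0.097, 0.164 and 0.233, which sum to 0.603. The weighted sum is 1×0.109 + 2×0.097 + 4×0.164 + 8×0.233 = 2.82, and 2.82 / 0.603 = 4.7 weeks.

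| Assumed median | True mean | Mean among healed Visit 1 wounds |
|---|---|---|
| 4 | 5.8 | 4.3 |
| 6 | 8.7 | 4.7 |
| 12 | 17.3 | 5.0 |

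The recorded mean barely moves while the true mean triples, because no time beyond 8 weeks can be recorded.

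**Step 3. What new wounds add (m = 6).** Assume further that new wounds are split equally over weeks 1, 2 and 4 and timed from first measurement. The share healed by week 8 is 1 − 0.5^((8−w)/6), which is 55%, 50% and 37%, with mean 47.5%. If new wounds make up a fraction s of all wounds, the pooled share healed is (1−s)×60.3% + s×47.5%.

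| New wounds as share of all | Pooled share healed | Pooled mean among healed |
|---|---|---|
| 0% | 60.3% | 4.68 weeks |
| 10% | 59.0% | 4.65 weeks |
| 25% | 57.1% | 4.60 weeks |
| 50% | 53.9% | 4.52 weeks |

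So new wounds lower the share healed by about 1 to 6 points and the mean among healed wounds by 0.03 to 0.16 weeks. Leaving out open Visit 1 wounds costs about 4 weeks (8.7 − 4.7).

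**Step 4. Outcome 2 under different wound sets (assumed areas).** Suppose one participant has a Visit 1 wound going from 10 to 4 cm² and a new week-4 wound going from 6 to 5 cm². Visit 1 wounds only gives (10−4)/10 = 60%. The average of each wound against its own first measurement is (60% + 16.7%)/2 = 38%. Total area against Visit 1 gives (10 − 9)/10 = 10%.

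**The case against.** The plan is not limited to healed wounds. Percent change in area can be computed for any wound with a later measurement, and a regression of percent area healed on time uses open wounds and unequal follow-up without censoring. The untyped regression could be a survival model, and the general clause could admit one. All of that is right. It confines the censoring gap to outcome 1 and to any simple share healed, but for those outcomes no suitable method is named.

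Four stronger readings are tempting, and the documents do not support them.

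- *Outcome 2 can be computed only for Visit 1 wounds.* It cannot have a full 8 weeks for later wounds, but the phrase may simply name the study window, and a new wound can be compared with its own first measurement.
- *Unknown onset is a special defect of new wounds.* Outcome 1 reads as time under the dressings, and Visit 1 wounds also opened at an unknown date.
- *New wounds would be unfairly compared with baseline wounds.* No such comparison is planned.
- *New wounds are the main source of bias.* Step 3 shows that they are the smaller part.

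It is also fair to say that the rates are assumed, and that this is a descriptive series with no success threshold. The plan does not state that it will average healed wounds only. That is what a simple mean does when no rule covers the others.

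**Conclusion.** The point holds for all wounds, and for outcome 1 chiefly. The schedule facts (8 weeks at most, and 7, 6, 4 or 0 for new wounds) and the absence of a rule come straight from the documents. The size is illustrative: with exponential healing at a median between 4 and 12 weeks, a mean over healed wounds understates the true mean by 1.4 to 12.3 weeks (5.8 − 4.3, which is 1.4 before rounding, and 17.3 − 5.0), and by about 4 weeks at median 6. Slower healing makes it worse. Pooling new wounds is a secondary effect, 1 to 6 points on the share healed at median 6, and is small unless new wounds are many. No error rate or decision is affected. What is at risk is the meaning of the reported healing time, so this is a matter to consider and not a fault that reverses a conclusion.

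**What to change.** Add to the Analytical Plan:

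- Every wound is timed from its first measurement under the study dressings and censored at its last visit if unhealed.
- Outcome 1 is summarised by Kaplan-Meier or an interval-censored estimate, since healing is seen only at visits, in place of a simple mean or proportion. Intervals allow for several wounds per participant. The plan should also say what counts as healed, because any healing time depends on it.
- The 8-week percent healing in outcome 2 is reported for wounds measured at Visit 1. New wounds are listed separately, each against its own first measurement.

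The cost is wording, plus a record of the visit at which each wound was first seen. The measurement form is not in the documents and may already hold this. No extra visits or measurements are needed. There are downsides: fewer wounds in the 8-week figure, imprecise estimates with 10 participants, and a reported healing time that will look less favourable. If fewer than half the wounds heal by week 8, as in the median-12 illustration, the median will not be reached and only the share healed by each visit can be given.
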